#### 5.1.1. *Intention to treat (ITT) analysis*

In the Intention-to-Treat analysis, all participants will be analyzed according to their administered allocation, even in case they show protocol violations prior to or during the study.

#### 5.1.2. *Per protocol (PP) analysis*

An analysis based on a “per protocol” approach will be conducted to assess the non-inferiority of treatments, as recommended for non-inferiority studies. Thus, analyses based on the subjects following the study protocol will be the main strategy of analysis adopted for the primary and secondary endpoints. In the per-protocol analysis only participants who received PEP as planned, have completed follow-up, and follow the protocol as planned are included.

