9. STATISTICAL ANALYSIS

The statistical analysis will be described in the statistical analysis plan (SAP), written by the biostatistician, which is binding and will be finalized before database lock or before any other analysis takes place.

9.1 Baseline characteristics:

Both an intention to treat (ITT) and a per-protocol (PP) approach will be used to define the analysis populations in both phase 2 and phase 3 studies. In the Intention-to-Treat analysis, all participants will be analyzed according to their randomized allocation, even in case they do not receive the randomized treatment, show protocol violations prior to or during the study.

In the per-protocol analysis only participants who received PEP as planned, have completed follow-up, and follow the protocol as planned are included.

In the phase 2 study, the PP population will be the primary analysis population as indicated for non-inferiority studies by the ICH-E9 guidelines. For the phase 3 study, the intention to treat will be the primary approach.

The number of participants screened and enrolled or excluded will be summarized according to reason for exclusion. Of the enrollees, the number of patients discontinued or lost to follow-up will be recorded by reason and time of discontinuation. These figures will be summarized in a CONSORT flow diagram.

Subjects in each treatment group will be described according to baseline characteristics. The description will be in terms of medians and interquartile ranges for continuous variables and using counts and percentages for categorical variables. Standard statistical tests of significance of imbalance in baseline characteristics will be performed.

9.2. Phase 2 study:

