### 3.1.2. Secondary outcomes

- Baseline ALT and AST results
- Baseline QTc prolongations
- Post administration QTc prolongation, ALT and AST results
- Frequency of potentially common adverse events such as gastro-intestinal (nausea, vomiting), nervous system-related (headache, dizziness) and cutaneous reactions
- Occurrence of any (serious)AEs

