***Treatment deviations***

---

1. Vomiting of allocated treatment	Major	
2. Dosage miscalculation	Minor/Major	Minor if less dose is given, major if larger dose is given

---

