***Follow-up deviations***

---

1. Missing visit or samples of QTc at 24h or ALT/AST at day 14	Minor/Major	Minor if a participant gives ALT/AST until the day 30 visit
--	-------------	---

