## **6. Statistical Methods**

### **6.1. Primary safety analysis**

The main objective about the difference in QTc between the two arms 24 hours after treatment administration will be assessed by calculating the 95% confidence interval for the difference.

Non-inferiority is established if the upper limit of a one-sided 95% confidence interval around the difference in means QTc 24 hours after treatment administration (BE-PEP - SDR-PEP) is below the non-inferiority limit of +10 ms.

Analysis of covariance (ANCOVA) or an equivalent regression model correcting for the baseline values of QTc will also be used to assess the primary objective. Alternatively, the individual difference scores will be calculated by subtracting the QTc values at baseline from the ones at day 1. The difference scores will be compared using a two-sample t-test.

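### The phase 2 SAP makes per-protocol the main set for adverse events and liver tests, so participants who vomit the dose drop out of the main vomiting result

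*SAP*

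**What the plan says.** SAP 5.1 adopts two sets for the safety analysis, called ITT and per-protocol (PP), and makes PP primary on the ground that this is a non-inferiority study. Section 5.1.2 extends that choice beyond QTc: "Thus, analyses based on the subjects following the study protocol will be the main strategy of analysis adopted for the primary and secondary endpoints". Protocol 9.1 agrees in general terms: "In the phase 2 study, the PP population will be the primary analysis population".

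The PP set is narrow: "only participants who received PEP as planned, have completed follow-up, and follow the protocol as planned are included". Table 1, which stands within 5.1.2, grades "Vomiting of allocated treatment" as major. For dosing errors it says "Minor if less dose is given, major if larger dose is given". For late samples it is lenient: "Minor if a participant gives ALT/AST until the day 30 visit".

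The secondary outcomes in SAP 3.1.2 are mostly safety outcomes. One entry begins "Frequency of potentially common adverse events such as gastro-intestinal (nausea, vomiting" and goes on to nervous-system and skin reactions. Others are post-dose ALT/AST and the occurrence of any (serious) adverse event. Neither the post-PEP part of SAP 6.2 nor SAP 6.3 on adverse events names a different population.

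The SAP's ITT set (5.1.1) keeps participants with protocol violations and analyses them by the treatment they received.

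**The concern.** The only reason given for making PP primary is non-inferiority. Only one endpoint has a margin: in SAP 6.1 the one-sided 95% upper limit for the mean QTc difference must be such that it "is below the non-inferiority limit of +10 ms". Adverse events and ALT/AST are described by arm and compared with tests for a difference, so the reason does not reach them.

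For vomiting, the same event is counted as an outcome and, when the dose is expelled, is a reason to leave the main set. If one regimen causes more vomiting, more of its events are removed, and the arms look more alike than they were.

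The dosing rule is also one-sided: a participant given too much drug leaves the main adverse-event, SAE and liver results, while one given too little has only a minor deviation. Read literally, someone who stops follow-up after an adverse event leaves as well.

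Phase 2 exists to establish safety, and SAP section 1 makes the resulting report the basis of the main publications. The result labelled as main would be the conditioned one.

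**Working it through.** **Which set each endpoint gets, as written**

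| Endpoint | Has a margin? | Main set | Effect of expelling the dose |
|---|---|---|---|
| QTc at 24 h (SAP 6.1) | Yes, +10 ms | PP | Leaves the set |
| Vomiting and other common adverse events (3.1.2, 6.3) | No | PP | Leaves the set; for vomiting, it is also the counted event |
| Any (serious) adverse event (3.1.2, 6.3) | No | PP | Leaves the set |
| ALT/AST on days 14 and 30 (3.1.2, 6.2) | No | PP | Leaves the set |

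**The plan's own figure.** Protocol 4.3 gives 99% power for QTc with 150 per arm, SD 20 ms, margin 10 ms and no true difference. The noncentrality is 10 / (20 × √(2/150)) = 4.33. At one-sided 5% this gives 99.6%, which reproduces the stated figure. If 10% of each arm left PP (135 per arm), the noncentrality is 10 / (20 × √(2/135)) = 4.11 and power is 99.3%. PP therefore costs QTc almost nothing, and keeping it there is not in dispute.

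**Effect on vomiting.** Let r be the proportion who vomit and s the share of them who expel the dose. Both are assumptions; the documents give neither.

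- Removed per arm = 150 × r × s. For r = 2% to 10% and s = 25% to 100%, this runs from 150 × 0.02 × 0.25 = 0.75 to 150 × 0.10 × 1 = 15.
- Vomiting rate left in PP = r(1 − s) / (1 − rs).

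For r = 10% and s = 50%: 0.05 / 0.95 = 5.3%. For r = 2% and s = 50%: 0.01 / 0.99 = 1.0%. The difference is 4.3 points, against 8.0 among all treated.

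Expected difference in points:

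| True rates | All treated | PP, s = 25% | PP, s = 50% | PP, s = 100% |
|---|---|---|---|---|
| 10% v 2% | 8.0 | 7.7 − 1.5 = 6.2 | 5.3 − 1.0 = 4.3 | 0 |
| 5% v 2% | 3.0 | 3.8 − 1.5 = 2.3 | 2.6 − 1.0 = 1.6 | 0 |

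Power of the planned Fisher test (two-sided 5%, 150 per arm; all-treated exact, PP by simulation):

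| True rates | All treated | s = 25% | s = 50% | s = 100% |
|---|---|---|---|---|
| 10% v 2% | 80% | 72% | 52% | 0% |
| 10% v 5% | 30% | 26% | 17% | 0% |
| 5% v 2% | 18% | 16% | 9% | 0% |

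At s = 100% every vomiting event is removed, so the PP rate is zero in both arms by construction.

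**The case against.** **The unconditioned analysis is already planned.** The SAP's ITT set keeps these participants. No text limits the monitoring board's review or the pause criteria to PP (Protocol 7.2.3 and 8, SAP 3.1.1). This stands: no data are lost and no stopping decision is shown to be affected. What remains is which result is labelled as main.

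**SAP 6.3 speaks of all adverse events and of a table of each reported one.** That can be read as complete reporting. But it names no population, so it does not displace the explicit choice in 5.1 and 5.1.2. If complete reporting was meant, the two sections need reconciling.

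**No sentence says that a major deviation means removal from PP.** This is true. Removal follows from the table's place in 5.1.2 and from the requirement to have received PEP as planned. The case is weaker for non-completers, because Table 1 tolerates ALT/AST as late as day 30.

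**The mechanism is shown only for vomiting.** This also stands. Nothing is computed for liver, skin, nervous-system or serious events. For ALT/AST the direction could even reverse, since people who expelled the dose presumably absorbed less drug. The argument for those endpoints is that the stated reason for PP does not apply and that over-dosed participants leave the main result.

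**The lead example is favourable to the concern.** At s = 5% to 10% the 8.0-point difference becomes only 7.6 to 7.3, with power about unchanged. In the smaller contrasts the test has little power in either set. The size is therefore uncertain; that PP shrinks a true vomiting difference does not depend on the rates chosen.

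**Conclusion.** The concern holds. As written, PP is the main set for adverse events, SAEs and ALT/AST as well as QTc, for a reason that applies only to QTc. The main vomiting comparison then excludes participants because they had the counted event, which pulls the difference between arms towards zero. Under assumed rates of 10% against 2%, the loss runs from under one point if few expel the dose to the whole 8.0 points if all do. These sizes rest on r and s, which the documents do not give. The effect on other adverse events and on liver tests is not quantified and its direction is not established. The consequence is confined to the planned report and the publications based on it. It should be fixed, but it does not threaten the conduct of the study.

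A lesser point lies beside it: SAP 5.1 and 5.1.1 define ITT by treatment administered, whereas Protocol 9.1 defines it by randomized allocation. The effect is probably small, because the envelope is drawn and the drug given together (Protocol 4.4), with observed intake (Protocol 6.2).

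**What to change.** 1. In SAP 5.1 and 5.1.2, and in the matching sentence of Protocol 9.1, limit PP as the primary set to the QTc non-inferiority comparison.
2. Rename the SAP's existing as-treated set as the safety set: everyone who took any study drug, by treatment received, regardless of vomiting, dosing error or completion of follow-up.
3. Name that set in SAP 6.2 (post-PEP results) and 6.3 as the main set for adverse events, SAEs, ALT/AST and the stopping-criteria outcomes. PP can remain as a supporting analysis, which is useful for ALT/AST, where expelled doses may dilute a drug effect.
4. State in 5.1.2 whether a major deviation in Table 1 removes a participant from PP, and what counts as completed follow-up.
5. As the lesser point, define ITT by randomized allocation as in Protocol 9.1 and report it beside PP for QTc.

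The cost is wording in SAP 5.1, 5.1.1, 5.1.2, 6.2 and 6.3 and one sentence in Protocol 9.1. It needs no new data and no extra participants. If the phase 2 database has already been locked, which the documents do not say, SAP section 1 requires the change to be described and justified in the analysis report instead.

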**Table 1: The protocol deviations classified as minor or major deviation**

Protocol Violation	Major/Minor Deviation	Comments
Inclusion criteria		
1. Being a permanent resident of the study village, in good state of health	Major	
2. Able and willing to provide informed consent	Major	
3. Age 5 years or above and weight of 20 kg or above.	Major	
Exclusion criteria		
1. Signs of active leprosy	Major	
2. Signs of active pulmonary tuberculosis (cough $\geq 2$ weeks duration)	Major	
3. Signs of active extra-pulmonary tuberculosis (bluish-red nodules that cover the lymph nodes, bones or joints, or cervical glands with discharge)	Major	
4. History of liver- or kidney disease	Major	
5. Allergy to rifampicin or bedaquiline	Major	
6. Having received rifampicin or bedaquiline (if applicable) in the last 2-year period	Major	
7. Not able to swallow bedaquiline 100 mg tablets	Major	

8. Self-reported (suspected) pregnancy or breastfeeding	Major
9. Concurrent (within the last three-week period before D0) use of medications not included in the safe list (for bedaquiline only)	Major
10 .QT-prolongation of $\geq 450$ msec in baseline ECG within the last week.	Major
11. Jaundice or self-reported liver function abnormalities or hepatitis	Major
12. Value of baseline ALT or AST $>3x$ ULN within the last week. In case only ALT is available, this would suffice for enrollment.	Major

---

***Treatment deviations***

---

1. Vomiting of allocated treatment	Major	
2. Dosage miscalculation	Minor/Major	Minor if less dose is given, major if larger dose is given

---

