4.3 Sample size

The sample size for the phase 2 trial is based on non-inferiority of the BE-PEP regimen compared to the SDR-PEP regimen in terms of adverse events, in particular QTc prolongation. We assume that in the SDR group the mean QTc will be equal to that of a reference population, i.e. 384 ms (SD 20 ms) based on the Fridericia correction method. [29]

The sample size calculations were performed by simulation, in a scenario where there is truly no difference between the standard and experimental treatment. A sample size of 64 patients are required per arm to achieve 80% power in the comparison that the upper limit of a one-sided 95% confidence interval will be below the non-inferiority limit of +10 ms.

For this part of the trial we have selected a village with a total recorded population of 908, 51% of whom are aged 18 years or above. As explained in chapter 4.2 above, as a matter of precaution we will first enroll adults and preliminarily assess their outcomes before we will start enrolling minors. The numbers of adults to be enrolled will be proportional to the observed age distribution at the time of the 2022 survey. To arrive at an accurate estimate of mean QTc for adults as well as for minors, we will recruit 150 participants per study arm, approximately 75 adults and 75 minors.

Overall, all ages combined, our intended sample size of 150 in each arm, which will provide 99% power to show that the upper limit of a one-sided 95% confidence interval will be below the non-inferiority limit of +10ms, assuming that in the larger population QTc does not differ between those receiving SDR-PEP and those receiving BE-PEP. Sample size calculations were done in R version 4.0.2.[30]

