## 5. Description of analysis populations

### 5.1. Analysis populations

For the safety analysis, both an intention-to-treat (ITT) and a per-protocol (PP) approach will be adopted. In both ITT and PP populations, participants will be analyzed according to their administered treatment. The PP population will be the primary analysis population as indicated for non-inferiority studies by the ICH-E9 guidelines.

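### SAP Table 1 grades an under-dose as minor and an over-dose as major, which conflicts with the SAP's own per-protocol definition and would tend to favour non-inferiority if QTc rises with bedaquiline exposure

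*SAP*

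**What the plan says.** SAP 5.1 sets the primary population for phase 2: "The PP population will be the primary analysis population as indicated for non-inferiority studies by the ICH-E9 guidelines". SAP 5.1.2 defines it: "only participants who received PEP as planned, have completed follow-up, and follow the protocol as planned are included". Table 1 follows within that section and grades each deviation as minor or major. Under treatment deviations it has two rows. "Vomiting of allocated treatment" is graded major without qualification. Dosage miscalculation is graded by direction: "Minor if less dose is given, major if larger dose is given". The row names neither the drug nor the arm. No sentence in the SAP says that a major deviation removes a participant from the per-protocol set or that a minor one does not.

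The primary comparison in SAP 6.1 is BE-PEP minus SDR-PEP in mean QTc at 24 hours. Non-inferiority requires that the "upper limit of a one-sided 95% confidence interval around the difference in means QTc" "is below the non-inferiority limit of +10 ms". SAP 5.1.1 also plans an ITT analysis in which "all participants will be analyzed according to their administered allocation, even in case they show protocol violations prior to or during the study".

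Protocol 7.1.3 attributes bedaquiline's QT risk mainly to the peak concentration of its M2 metabolite, through an Emax relation. Bedaquiline is given as 400 or 800 mg by weight, and the schedule in Protocol 5.1 steps between the two at 30 kg. A wrong band at that step would halve or double the bedaquiline dose.

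**The concern.** The endpoint is a harm that is expected to increase with exposure. A per-protocol set is made primary in a non-inferiority test so that departures from treatment do not make the arms look alike. Under-dosing of the experimental arm is such a departure, yet it is the direction that Table 1 treats as harmless. Vomiting also lowers exposure and is graded major in the row above, and the SAP gives no reason for the difference.

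If Table 1 decides membership, the primary set is selected by the direction of the dose error. If the text of 5.1.2 decides it, the minor grade contradicts that text, because an under-dosed person did not receive treatment as planned. Either way the primary population is not uniquely defined, and the choice could be made after the data are seen. At stake is the QTc contrast that the DSMB will weigh before phase 3.

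**Working it through.** **Inputs.** Margin +10 ms and a one-sided 95% limit (SAP 6.1); QTc "384 ms (SD 20 ms) based on the Fridericia correction method" (Protocol 4.3); 150 per arm (both documents). From Protocol 7.1.3: M2 Emax 28.6 ms, EC50 855 ng/mL, predicted worst-case M2 peak below 130 ng/mL after two doses, with 50% accumulation assumed. No document gives a dose-error rate, so the fraction f below is an assumption.

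**1. The plan's own figures.** With a true difference of zero, n per arm = 2 × SD² × (z for alpha + z for power)² / margin².
- One-sided 5%: 2 × 400 × (1.645 + 0.842)² / 100 = 49.5, so 50.
- One-sided 2.5%: 2 × 400 × (1.960 + 0.842)² / 100 = 62.8, so 63. With the t distribution, 64 per arm gives 80.1% power.

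The stated 64 therefore matches a one-sided 2.5% test. With 150 per arm, power is 99.6% at one-sided 5% and 99.1% at 2.5%, in line with the stated 99%. The steps below use the SAP's one-sided 5% rule.

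**2. Precision.** SE = 20 × √(2/150) = 2.309 ms. The half-width is 1.645 × 2.309 = 3.80 ms, so non-inferiority needs an observed difference below 6.20 ms.

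**3. Half-dose errors kept in the set, true effect at the margin.** Assume 10 ms at full dose, an effect proportional to dose, and a fraction f of BE-PEP recipients at half dose. The mean difference is (1 − f) × 10 + f × 5 = 10 − 5f. The chance of declaring non-inferiority is Φ(5f / 2.309 − 1.645).

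| f | Shift (ms) | Under-doses kept | Under-doses excluded |
|---|---|---|---|
| 1% | 0.05 | 5.2% | 5.0% |
| 2% | 0.10 | 5.5% | 5.0% |
| 5% | 0.25 | 6.2% | 5.0% |
| 10% | 0.50 | 7.7% | 5.0% |

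**4. Errors in both directions.** Add the same fraction f at double dose (20 ms under proportionality). Under the Table 1 reading, the mean at f = 5% is (0.90 × 10 + 0.05 × 5) / 0.95 = 9.74 ms, with SE = 20 × √(1/150 + 1/142.5) = 2.340 ms.

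| f in each direction | Table 1 reading | Both excluded | All kept |
|---|---|---|---|
| 5% | 6.3% | 5.0% | 4.0% |
| 10% | 7.9% | 5.0% | 3.1% |

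Removing over-doses does not bias the estimate of the planned-dose effect. The departure from 5.0% comes from keeping the under-doses.

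**5. The protocol's exposure-QT figures.** Effect = 28.6 × C / (855 + C). Dividing out the 50% accumulation, the single-dose peak is 130 / 1.5 = 86.7 ng/mL.
- Full dose: 28.6 × 86.7 / 941.7 = 2.63 ms.
- Half dose: 28.6 × 43.3 / 898.3 = 1.38 ms.
- Shift with 5% at half dose: 0.05 × (2.63 − 1.38) = 0.06 ms, against an SE of 2.31 ms.
- With 5% half and 5% double dose (4.82 ms), the mean difference is 2.57 ms under the Table 1 reading, 2.63 ms with both excluded and 2.68 ms with all kept.

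**6. Precision lost by excluding.** With no drug effect and 5% errors in each direction, the expected upper limit is 3.80 ms with all kept, 3.85 ms under the Table 1 reading and 3.90 ms with both excluded.

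**The case against.** Four points on the other side have force.

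First, the link from grade to population is implied, not written. The only stated membership rule is in 5.1.2, and read literally it already excludes under-dosed participants. This stands. What is established is a conflict between the table and the text, with a natural reading of the table that is asymmetric.

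Second, a reader might infer that the rule can act only towards non-inferiority, whatever the dose error. The documents do not support that. The row covers either drug and either arm. A rifampicin error may leave QTc unchanged, and in the SDR-PEP arm it could act the other way if rifampicin affected QTc. Excluding people also widens the interval slightly.

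Third, a reader might infer that the false-positive rate is above 5% in this trial. That requires bedaquiline dose errors to occur at a material rate. Phase 2 gives one directly observed dose, recorded in REDCap, with a doctor present. At 1% to 2% errors the excess is 0.2 to 0.5 percentage points. The 10 ms stress case is also far from the protocol's prediction: it would need M2 at 8550 / 18.6 = 460 ng/mL, above the 361 ng/mL quoted for steady state in tuberculosis treatment. The margin is still where a false claim of non-inferiority has to be assessed, so both calculations belong here.

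Fourth, the ITT analysis by administered treatment keeps dose errors in both directions. The DSMB judges the clinical relevance of any QTc prolongation (Protocol 8), and the QTc pause criterion is not confined to the per-protocol set. The result is therefore not a mechanical gate. However, the ITT set also keeps the under-dosed, it is not primary, and nothing requires it to agree with the per-protocol result.

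**Conclusion.** The point holds as an asymmetric grading that conflicts with the per-protocol definition and with the grading of vomiting. On the natural reading of Table 1 it shapes the primary population. The expected direction, towards non-inferiority, rests on three conditions: the error is in bedaquiline, it is in the BE-PEP arm, and QTc rises with exposure. Protocol 7.1.3 supports the third.

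The likely size is small: a few hundredths of a millisecond on the protocol's exposure-QT figures at 5% errors. In the dose-proportional stress case at the margin, a nominal 5% becomes 6.2% at 5% half-dose errors and 7.7% at 10%. It should be corrected because the primary set ought to be fixed before database lock and the change is cheap. The documents do not show that the error rate of this trial is inflated.

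**What to change.** In SAP Table 1, grade a dose error in either direction as major for the per-protocol QTc analysis, consistent with 5.1.2. Add one sentence to 5.1.2 stating that participants with a major deviation leave the per-protocol set and that those with only minor deviations stay. Name the already planned ITT analysis by administered treatment as the supporting QTc contrast, and tabulate dose errors by drug, arm and direction so that a reader can see whether the handling matters.

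The cost is one table cell, one sentence and one small table. A few participants may leave the per-protocol set, and the interval widens slightly: about 0.05 ms on the upper limit relative to the Table 1 reading (3.90 against 3.85 ms) at 5% errors in each direction with no drug effect. The change concerns classification for analysis only and alters no dosing or clinical procedure.
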